The PRAC initiated a subsequent benefit-risk evaluation and considered that the controlled clinical studies required by the Note for guidance on clinical investigation of medicinal products for treatment of nociceptive pain (CPMP/EWP/612/00, issued 21 November 2002) for long-term treatment of chronic pain are not available for flupirtine-containing medicinal products². Based on the fact of observed liver effects recorded during long-treatment with Flupirtine and on the absence of controlled long-term clinical studies, the PRAC noted that the management of chronic pain is no longer favourable in terms of the benefit-risk balance for flupirtine-containing medicinal products. The PRAC adopted a recommendation on 13 June 2013 under the provisions of article 107i of Directive 2001/83/EC³.

Taking the currently available data into account, the PRAC decided that the benefit-risk balance for flupirtine-containing products is favourable in the treatment of acute pain, subject to implementation of the following risk minimisation measures⁴:

- Limitation of indication to acute pain in adults if treatment with other analgesics (e.g. NSAIDs, weak opioids) is contraindicated.
- Restriction of Flupirtine use to a maximum of two weeks of treatment.
- Contraindication of Flupirtine in patients with pre-existing liver disease or alcohol abuse.
- Contraindication of Flupirtine in patients concomitantly taking other medications which are known to cause Drug Induced Liver Injury (DILI).

- Weekly liver function tests during treatment and discontinuation in the case of abnormal liver function tests or clinical symptoms.

The PRAC imposed a DHPC, which was distributed on 15 July 2013, in order to communicate the outcome of the PRAC/EMA decision to healthcare professionals⁵. The SmPCs for flupirtine-containing medicinal products have been revised accordingly by Lupin in February 2014 and MAHS marketing flupirtine-containing medicinal products in September/October 2013⁶. The educational material was distributed in February 2015.

Patients and prescribers have been provided with joint educational material according to the PRAC request, prepared jointly by all German MAHs. The educational material, the DUS and a PASS protocol are parts of the RMP.

As of 5 September 2013, the European Commission implemented the decision (C(2013) 5788 final) with the majority opinion of the CMD(h) addressed to all member states based on the PRAC's recommendation⁷.

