9.2. Setting

The study will be conducted in the outpatient setting in Germany.

Study population

All patients with a record of Flupirtine prescription during the defined 12-month periods (patient selection window) will be identified from selected database.

The study will include both single users and recurrent users of flupirtine-containing medicinal products.

The study will include two cohorts of patients:

- patients initiated on flupirtine treatment after the review of SmPC in Germany
- patients treated with flupirtine before the review of SmPC in Germany

The two cohorts will include:

- Incident user: patients who had one or more flupirtine prescriptions during the one-year observational period, but no flupirtine prescription for at least 12 months prior to the first flupirtine prescription during the observational period
- Prevalent user: patients who had one or more flupirtine prescriptions during the one-year observational period and at least one flupirtine prescription during the 12 months prior to the first flupirtine prescription during the observational period

Inclusion criteria:

Eligible patients must have at least one prescription of Flupirtine (exposure) during the defined 12-month observational period.

Exclusion criteria:

Exclusion criteria will not be applied.

Study period

The selection of patients from the IMS[®] Disease Analyzer will be carried out in two defined 12-month periods from January 1, 2012 to December 31, 2012 and January 1, 2014 to December 31, 2014, respectively (patient selection window). The date of the first prescription fill in each period will be defined as the exposure start date.

Pre-exposure period:

In order to obtain information about medical history before Flupirtine exposure start, a time period of at least 12 months prior to the individual Flupirtine exposure start date will be analysed for each patient for whom these data are available.

Follow-up:

A follow-up period of one to six months after the exposure start date will be monitored for all patients, and till the end of analysis period for whom these data are available.

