9.7 Data analysis

9.7.1 General remarks

Data from specialist panels will not be combined. The data will be analysed separately by panel (PCP and orthopaedist panel) and for the period before and after SmPC review.

All analyses will be stratified by incident and prevalent users.

Study tables will reference the data source used for each set of results. The data will be presented graphically where useful.

The statistical unit will be the patient (for information such as demographical and clinical characteristics, medical history, contraindications) and the Flupirtine prescription (for information such as indication, number of prescriptions, recommended treatment duration, concomitant drug prescriptions).

The statistical analysis will be done descriptively. Missing values will be reported as missing and no imputation will be conducted. Descriptive tables will be compiled for all variables. Continuous variables will be presented with counts, means, medians, standard deviations, and minimum and maximum values. Categorical variables will be presented in frequency tables. Rates and 95% confidence intervals will be provided when relevant.

Data will be analysed using the statistical software SAS (SAS Institute Inc., Cary, USA) with version 9.3 or above.

All results will be presented in tables. In addition, parameters addressing the primary objectives and eligible for a comparison of time periods (assessment period and reference period) with respect to the effect of risk minimisation measures (for example flupirtine treatment duration) will be presented graphically e.g. by displaying plots or bar charts.

The following section will describe the analyses and definitions used for the DA (**IMS[®] Disease Analyzer**) database.

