9.7.2.1 Patient characteristics of Flupirtine treated patients

The patient characteristics (age, gender, insurance private or SHI) of Flupirtine patients will be described.

- Number of patients within following age groups:
 - < 18 years
 - 18 to 29 years
 - 30 to 39 years
 - 40 to 49 years
 - 50 to 59 years
 - 60 to 69 years
 - 70 years and older

Analyses:

- Number and percentage of Flupirtine patients per age group, gender, insurance status(private or SHI insured)

Indication for flupirtine prescription

In order to describe the indication for flupirtine drugs all diagnoses related to the flupirtine prescriptions will be analysed.

- All diagnoses documented on the prescription of flupirtine will be defined as principal diagnosis.

As not for all prescriptions principal diagnoses will be available, additionally the following approaches will be chosen:

- If there is any disease associated with acute pain (Annex 3-ii) recorded in a time frame of 2 weeks around the date of prescription, this will be defined as associated diagnosis.
- If there is any disease associated with acute pain (Annex 3-ii) recorded in a 12 months history before the date of prescription, this will be defined as co-morbidity.

Principal diagnoses, associated diagnoses and co-morbidities will be analysed separately.

The findings of principal diagnoses will be grouped by diagnosis according to ICD-10 codes (selection of codes see Annex 3) including diseases associated with acute pain and chronic pain.

Analysis:

- Number and percentage of prescriptions, stratified by diagnosis (only principal diagnoses)
- Number and percentage of prescriptions associated with acute pain (principal diagnoses, associated diagnoses and co-morbidities)
- Number and percentage of prescriptions associated with chronic pain (only principal diagnoses)

Contraindication for the use of NSAIDs or weak opioids

The patients' history will be evaluated for medical events referencing to contraindications for NSAIDs or weak opioids (such as myocardial infarction or stroke) for a timeperiod of 12 months prior to first prescription of Flupirtine. Only patients with a history of at least 12 months will be included in this analysis.

Analyses:

- Number and percentage of patients identified as contraindicated of NSAIDs/weak opioid treatment (such as myocardial infarction or stroke)

Long-term medications leading to contraindications for Flupirtin

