9.7.2.2 Flupirtine exposure

Flupirtine exposure will be defined as one or more prescriptions of Flupirtine. These prescriptions will be identified using the ATC code for Flupirtine or INN. The Flupirtine exposure start date (i.e. the cohort entry date) for each patient will be defined as the date of the first record of Flupirtine prescription during each of the defined twelve-month patient selection window.

Treatment duration

The treatment duration (in days) will be evaluated by using the recommended treatment duration by the physician. If this is not available, the treatment duration cannot be determined exactly as the dose recommendation “as required (pro re nata)” is very often given in the therapy of acute pain. Therefore, the percentage of patients with no information according to recommendation by the physician will be determined.

Prescription length

The prescription length (in days) will be determined as follows:

- For prescriptions with available information on recommended dose per day: from the prescription date plus the expected number of days of drug supply based on the package size and the recommended daily dose
- For all prescriptions without recommendation of dosage: from the prescription date plus the expected number of days of drug supply based on the package size and the DDD(400 mg / day)

The prescription length is therefore not necessarily identical to the treatment duration.

The following parameters will be considered in the analysis for each Flupirtine prescription:

- Date of prescription
- Recommended daily dose by physician
- Recommended treatment duration by physician

Analyses:

- Number and percentage of patients with prescriptions of a flupirtine-containing medicinal product during the 12-month patient selection window
- Treatment duration in days
- Prescription length
- Single use and repeated use

Treatment episodes

A treatment episode will be defined as one or more prescriptions (repeated prescriptions) of flupirtine with gaps between prescription length not more than 7 days. In the case the gap between the prescriptions is longer than 7 days it will be considered as two subsequent treatment episodes. The analysis of treatment episodes will consider prescription length based on DDD, because for all prescriptions this information will be available.

Analyses:

- Number and percentage of episodes
- Min, max, mean, median length of episodes
- Patients within each episode

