9.7.2.4 Comparison of the patient/prescriptions of the two observational periods

The comparison of the patients/prescriptions of the two observational periods (assessment period and reference period) based on IMS[®] Disease Analyzer data will consider the following parameters. The comparisons will be performed separately by physician panel and will be stratified by incident and prevalent users:

- Number and percentage of patients with any diagnosis of disease contraindicated for NSAIDs or weak opioids
- Number and percentage of prescriptions with diagnosis associated with acute pain
- Number and percentage of patients with single and repeated flupirtine prescriptions within the defined time period
- Number and percentage of prescriptions with LFT monitoring during flupirtine treatment
- Length of treatment episodes
- Number and percentage of patients with at least one treatment episode longer than 14 days (based on DDD)

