9.9. Limitations of the research methods

IMS[®] Disease Analyzer is representative of Germany as a whole insofar as that the included practices are selected to adequately reflect geographic coverage and differences between urban and rural locations. This database contains information from approximately 3,000 office-based physicians (including specialists) who represent approximately 2.4% of all practices in Germany. The balance of various specialties in the IMS[®] Disease Analyzer does not, however, exactly reflect the balance in Germany. The lack of data from Flupirtine-prescribing oncologists will limit only to some extent the representativeness of results. For the characterization and comparison of the prescribing practice, however, this does not pose a problem.

The limitations of the IMS[®] Disease Analyzer are those of a provider-sourced EMR database. Patients seeking care outside the EMR practice setting will not have that utilisation recorded in the database. One of the main reasons for data documentation is reimbursement purposes. In the IMS[®] Disease Analyzer patients cannot be tracked across panels. Therefore, patients cannot be followed up across specialties and double counting of patients cannot be completely ruled out when analyzing more than one panel. It is planned to use of the PCP and the orthopaedist panels for this study.

For patients covered in the IMS[®] Disease Analyzer the medical history of patients will be evaluated for at least 12 months.

The duration of Flupirtine treatment (in days) will be evaluated using the treatment duration recommended by the physician. In cases where this information is not available, the treatment duration will be calculated using recommended dosage by the physician. The dose recommendation “on demand (pro re nata)” is very often given in the therapy of acute pain, acute pain episodes, and acute pain exacerbations which occur repeatedly. Therefore, the actual treatment duration is often shorter compared to the length of prescription.

The length of prescription will be determined from the recommended daily dose by the physician (if available) or using the defined daily dose (DDD). The dose recommendation “on demand” will not be taken into account for the determination of prescription length.

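### The look-back for NSAID or weak-opioid contraindications stops before the prescribing date and at 12 months, so the reported proportion is understated in both periods

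*Protocol*

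**What the plan says.** The only operational rule for this measure is in protocol section 9.7.2.1. Contraindicating events are sought "for a timeperiod of 12 months prior to first prescription of Flupirtine", and "Only patients with a history of at least 12 months will be included in this analysis". Section 9.7.2.2 sets the anchor, defining exposure start as "the date of the first record of Flupirtine prescription during each of the defined twelve-month patient selection window". Section 9.7.1 makes the patient the unit of analysis for contraindications.

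The measure stands for one part of the restricted indication, which section 7 gives as "Limitation of indication to acute pain in adults if treatment with other analgesics (e.g. NSAIDs, weak opioids) is contraindicated". Section 9.7.2.4 lists it first among the parameters to be compared between 2012 and 2014: "Number and percentage of patients with any diagnosis of disease contraindicated for NSAIDs or weak opioids". No window is stated there.

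Elsewhere the history is described more broadly. Section 9.2 says that "a time period of at least 12 months prior to the individual Flupirtine exposure start date will be analysed" where data exist, and section 9.9 says that "the medical history of patients will be evaluated for at least 12 months".

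**The concern.** The rule closes the window at both ends. At the near end, a record dated the same day as the prescription is not before it, so a contraindication documented at the prescribing visit is scored as absent. At the far end, a stroke coded 15 months earlier and not coded again is scored as absent. The indication rule in the same section behaves differently: it uses diagnoses on the prescription itself and within two weeks around its date.

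This percentage is the plan's only direct measure of whether flupirtine goes to patients who cannot use other analgesics. Every missed contraindication in 2014 makes a patient treated within the restriction look like one treated outside it. The same loss affects the 2012 to 2014 difference, which is what the pre-post design is meant to show.

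**Working it through.** **The plan's own figures.** Table 2 (section 9.5) gives the patients with at least 12 months of history, who form the denominator here, and reduces them by 25%.

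- PCP panel: 11,284 × 0.75 = 8,463 (stated 8,463).
- Orthopaedist panel: 1,821 × 0.75 = 1,365.75 (stated 1,365).

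Both reproduce. The share of patients with 12 months of history is 11,284 / 14,743 = 76.5% for PCPs and 1,821 / 4,635 = 39.3% for orthopaedists. The text rounds the expected sizes to about 8,400 and 1,300, used below.

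**Three records under the rule as written**

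| Contraindicating record | Scored as |
|---|---|
| 6 months before the first in-window prescription | present |
| Same date as that prescription | absent, on the literal reading |
| 15 months before, not coded again | absent |

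**Effect on one period's proportion.** Let p be the true proportion contraindicated and s the share of those patients whom the window captures, with no false positives. The table shows p × s, and the understatement is p × (1 − s). The documents give neither quantity, so both are assumptions: p from 20% to 60%, s from 0.5 to 0.9.

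- Smallest: 20% × 0.1 = 2 points.
- Middle: p = 40%, s = 0.7 shows 28%, so 12 points are missed.
- Largest: 60% × 0.5 = 30 points.

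The 95% confidence half-width is 1.96 × √[ps(1 − ps)/n]. At ps = 0.28 it is 0.96 points for n = 8,400 and 2.44 points for n = 1,300. Over the whole grid it is about 0.6 to 1.1 and 1.6 to 2.7 points. The printed intervals would not reveal a loss of the middle size.

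**Where s might lie, far end only.** Assume each patient's event is spread evenly over the previous Y years and that older events are coded again in the last 12 months with probability q. Then s = 1/Y + (1 − 1/Y)q.

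| | q = 0.3 | q = 0.6 | q = 0.9 |
|---|---|---|---|
| Y = 3 | 53% | 73% | 93% |
| Y = 10 | 37% | 64% | 91% |

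The result depends mainly on q, which the documents do not give. With frequent re-coding the loss is under 10% of cases.

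**Effect on the comparison.** The observed difference is s₂p₂ − s₁p₁.

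- Equal capture: it becomes s(p₂ − p₁). A true 10-point rise shows as 5, 7 or 9 points at s = 0.5, 0.7 or 0.9.
- Unequal capture with no true change, p = 40%: s moving from 0.7 to 0.8 gives 28% against 32%, a spurious rise of 4 points. From 0.7 to 0.6 it gives 28% against 24%, a spurious fall of 4 points.

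**The case against.** The best defence is that a fixed 12-month window, limited to patients with that much history, gives both years the same chance of finding a record. It matches the incident/prevalent definition and the 12-month co-morbidity look-back in the same section. This stands, and it is why the 12-month row should remain the main one.

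It can also be said that whether the index date counts is a detail for the statistical analysis plan, and that section 9.7.2.1 separately tabulates concomitant diseases around flupirtine treatment. The protocol does not explicitly exclude the index date, so that part of the point rests on its literal wording. But the wording is there to be programmed, and the concomitant-disease table is not linked to this measure.

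The apparent conflict between sections can be read away: 9.2 and 9.9 may describe available history in general, and the listing in 9.7.2.4 may mean any of the relevant diseases rather than at any time. That is a fair reading, but the text does not settle it.

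Four stronger readings are tempting and not supported:

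- **Off-label use is overstated in both years.** The restriction was recommended in June 2013 and entered product information from September/October 2013. In 2012 there was no such limit to breach.
- **The comparison is biased towards no change.** That holds only if capture is equal or worse in 2014. It is plausible, but unproven, that prescribers began recording the reason at the visit.
- **Status should be reassessed at every prescription.** Section 9.7.1 says "The statistical unit will be the patient (for information such as demographical and clinical characteristics, medical history, contraindications"), and status at cohort entry is coherent with that. Counting a patient as positive at any prescription would give repeat users more chances to be flagged, and repeat use is itself a compared parameter.
- **A contraindication never lapses.** The documents do not say so. Infarction and stroke are given only as examples.

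**Conclusion.** The point holds as one about ascertainment. As written, the rule misses contraindications recorded on the prescribing date and older ones not coded again, so the proportion is understated in both periods. In 2014 this makes use outside the restricted indication look more common than it is. The conclusion assumes that some records fall in those two gaps and that at least some older events still count as contraindications.

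The size cannot be fixed from the documents; 2 to 30 points is an assumption range, not an estimate. A true change is attenuated if the missed share is equal in both periods, and otherwise the bias could go either way. The study is descriptive, so no test or threshold turns on the figure. The change is still worth making, because it is cheap and this is the only direct measure of that restriction.

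**What to change.** - In 9.7.2.1, define the window as the 12 months up to and including the date of the first in-window flupirtine prescription. Keep this as the main row, one classification per patient.
- Add one sensitivity row with a longer look-back of the same fixed length in 2012 and 2014, among patients with that much history. Show the 12-month result for the same patients beside it, so that a change of window is not mixed with a change of population.
- State the same definition in 9.7.2.4, and reconcile it with the broader history wording in 9.2 and 9.9.
- Do not add per-prescription reassessment to the patient-level comparison.

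The cost is a wording change and a little extra tabulation, with no new data collection. The sensitivity row will cover fewer patients, most of all in the orthopaedist panel, where only 1,821 of 4,635 have even 12 months of history. The protocol gives no counts for longer histories, so a feasibility count should come before the length is fixed.

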Flupirtine, a non opiotic analgetic drug for acute and chronic pain relief was first introduced in the European Union in 1984 as an alternative analgesic to opioids and NSAIDs. During the use of this selective neuronal potassium channel opener (SNEPCO) other pharmacological impacts such as a reduction in muscle tension have been observed.

The German Federal Institute for Drugs and Medical Devices (BfArM) induced an urgent union procedure under Article 107i of Directive 2001/83/EC on February, 28th 2013 and signaled its intention to restrict the use of all flupirtine-containing

medications to short term treatment of acute pain and to withdraw the indication of use in chronic pain¹.

This intention from BfArM was based on a rising number of observed liver effects spontaneously reported during Flupirtine treatment while evaluating pharmacovigilance data. The effects range from asymptomatic liver enzyme elevation to fatal liver failure or liver transplantation were received. BfArM reported a total number of 954 records in their German adverse drug reaction database for Flupirtine including 330 reports for the system organ class (SOC) hepatic and biliary disorders (according to Common Terminology Criteria for AEs, CTCAE). Liver failure was reported in 49 cases including 12 cases with fatal outcome and 3 cases with liver transplantation. Flupirtine treatment lasted 60 days in average. In 25 of the above 49 cases (51%) a co medication with potential hepatotoxic effect was administered.

The growing number of Flupirtine prescriptions in Germany and thus the steadily increasing patient exposure was embraced to be associated with the rising number of reported Adverse Drug Reactions (ADRs). Additionally, a lack of the minimum requirement in the efficacy data of Flupirtine of at least three months treatment in controlled clinical studies for mild to moderately severe chronic nociceptive pain was denounced by the BfArM².

Considering the above safety concerns and further consideration of the current evidence for the efficacy of Flupirtine in the treatment of acute and chronic pain, the BfArM came to the conclusion, that the benefit-risk balance was potentially favourable in acute pain, implementing strict treatment restrictions (e.g. treatment duration limited to 2 weeks, frequent liver tests) and unfavourable in the treatment of chronic pain.

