Additionally the PRAC requested that the MAHs should submit a risk management plan (RMP) within 3 months after the EC decision. The protocols of two studies - a drug utilization study (DUS) and a PASS should be submitted as part of the RMP.

Hormosan Pharma GmbH launched Flupirtinmaleat-Hormosan 100 mg Hartkapseln in Germany on 31 July 2012, but the marketing of the product was stopped in January 2013. This decision was taken because of commercial and not for safety reasons. Any other MAs held by Lupin Group of companies within EU have not been launched yet. Therefore an extension of deadline for submitting the RMP (including the outline of DUS, PASS and educational material) was received by the Reference Member State (RMS) authority BfArM on 29 November 2013 as the products are currently not marketed.

This protocol covers a design for a DUS based on the information captured in longitudinal patient-level databases and has been designed to fulfill the conditions of the authority.

8. Research question and objectives

The Flupirtine DUS aims to characterise prescribing practices of flupirtine-medicinal products during routine clinical use and to assess the main reasons for prescription by representative groups of prescribers.

The analysis will display by specialty and by prevalent/incident status:

- Number of prescribing physicians
- Region of office (East/West Germany)
- Number of overall patients in the office
- Number of patients with at least one flupirtine containing product

- Patient characteristics: age, gender, insurance status, indication for Flupirtine prescription
- Flupirtine exposure:
 - Number of Flupirtine prescriptions per patient during the 12-month observation period
 - Recommended daily Flupirtine dose (by physicians)
 - Recommended Flupirtine treatment duration (by physicians)
 - Prescription length
 - Indications related to the Flupirtine prescription
 - Co diagnosis within analysis period
 - Concomitant prescription of drugs grouped by relevant ATC classes (Annex 3- ii)
- Administered long-term medications (>14 days) leading to contraindication use of Flupirtine
- Contraindications for use of NSAIDs or weak opioids
- Treatment patterns if available
- Liverfunctions test performed within 1 week after Flupirtine exposure start

9. Research methods

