A therapy duration exceeding 14 days will be considered as long-term treatment within a year time span. A long-term treatment known to lead to contraindications for the use of Flupirtine will be analyzed

Analyses:

- Number and percentage of long-term therapies leading to contraindication of Flupirtine

Concomitant diseases of Flupirtine patients

Diseases are assumed to be concomitant, if prescription issued prior or after 2 weeks to Flupirtine treatment within study period.

Analyses:

- Number and percentage of patients with concomitant diseases during observation period, grouped by ICD codes

Therapies related to Flupirtine treatment

Patients treated with Flupirtine will be monitored by analyzing all co-prescriptions within the observation window of 12 months prior to Flupirtine treatment start, grouped by diagnosis according to ICD-10 codes [selection of codes see Annex 3 (ii)].

Analyses:

Number and percentage of patients receiving co-medication during 12 months prior to Flupirtine treatment start grouped by diagnosis according to ICD-10 codes [selection of codes see Annex 3 (ii)].

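### Contraindicated hepatotoxic co-medication is measured as any therapy over 14 days in an unanchored year, not as use overlapping flupirtine, and no flupirtine contraindication is in the pre-post comparison list

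*Protocol*

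**What the plan says.** Section 7 lists the risk minimisation measures. Three matter here:

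- "Contraindication of Flupirtine in patients concomitantly taking other medications which are known to cause Drug Induced Liver Injury (DILI").
- "Contraindication of Flupirtine in patients with pre-existing liver disease or alcohol abuse".
- "Restriction of Flupirtine use to a maximum of two weeks of treatment".

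Section 9.7.2.1 turns the first into an analysis with the rule "A therapy duration exceeding 14 days will be considered as long-term treatment within a year time span". The planned output is "Number and percentage of long-term therapies leading to contraindication of Flupirtine". The same section specifies a co-prescription analysis, described as "analyzing all co-prescriptions within the observation window of 12 months prior to Flupirtine treatment start" and grouped by the diagnosis codes in Annex 3 (ii).

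Concomitant medication also appears elsewhere. It is an extracted variable in the abstract and in section 9.3, section 8 has "Concomitant prescription of drugs grouped by relevant ATC classes (Annex 3- ii"), and section 9.7.1 makes the flupirtine prescription its unit of analysis. None of these places gives a time window.

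Liver disease and alcohol abuse are not named in the objectives, the variables or the analyses. Section 9.7.2.1 has a general table of concomitant diseases by ICD code. Section 9.7.2.4 lists six parameters for comparing 2012 with 2014: NSAID or weak-opioid contraindication, acute-pain diagnosis, single versus repeated prescriptions, liver function monitoring, episode length, and episodes over 14 days.

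**The concern.** Section 9.1 sets the study up to compare prescribing before and after the SmPC revision. Whether flupirtine is still given together with hepatotoxic drugs is one of the main things to learn. The protocol shows why in section 7: "In 25 of the above 49 cases (51%) a co medication with potential hepatotoxic effect was administered".

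The planned rule can be wrong in both directions. It also responds poorly to the change it should detect. If prescribers in 2014 no longer let a hepatotoxic course run alongside flupirtine, the earlier course still counts whenever it exceeded 14 days and fell in the chosen year. Because flupirtine itself is limited to two weeks, short courses taken alongside it are an important part of the exposure, and the rule cannot record them.

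**Working it through.** **The plan's own figure.** 25/49 = 0.510, which reproduces the stated 51%. It shows that the topic matters. It comes from spontaneous reports of liver failure and does not measure misclassification among flupirtine users.

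**Restriction and measure side by side**

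| Element | Restriction (section 7) | Measure (section 9.7.2.1) |
|---|---|---|
| Timing | At the same time as flupirtine | Any time in a year, anchor not stated |
| Duration | No minimum | More than 14 days |
| Unit | Patient | Therapy, denominator not stated |

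Section 9.7.1 names the patient as the statistical unit for contraindications, so the counted unit in section 9.7.2.1 also conflicts with the protocol's own general rule.

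**Three example patients**

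1. A 21-day hepatotoxic course that ended months before flupirtine: counted, but not concomitant.
2. A 10-day course taken during flupirtine: concomitant, but not counted.
3. A 180-day course spanning flupirtine: concomitant and counted.

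**How often a flagged therapy would overlap.** The protocol gives no durations, so this is an illustration. It assumes one flupirtine course of 14 days and one hepatotoxic therapy of L days (L > 14), with random placement. Overlap means at least one shared day. The year is not anchored, so two readings are shown.

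*Reading A: both courses lie wholly inside the same 365-day span.* Flupirtine has 365 − 14 + 1 = 352 possible start days and the therapy has 366 − L. The pairs without overlap number (352 − L)(353 − L), so

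share overlapping = 1 − (352 − L)(353 − L) / [352 × (366 − L)].

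- L = 15: 1 − (337 × 338)/(352 × 351) = 1 − 113,906/123,552 = 7.8%.
- L = 300: 1 − (52 × 53)/(352 × 66) = 1 − 2,756/23,232 = 88.1%.

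*Reading B: the therapy starts on one of the 365 days before flupirtine start.* It overlaps if it is still running on the first flupirtine day, so

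share overlapping = (L − 1)/365.

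- L = 15: 14/365 = 3.8%.
- L = 300: 299/365 = 81.9%.

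| L (days) | Reading A | Reading B |
|---|---|---|
| 15 | 7.8% | 3.8% |
| 30 | 12.1% | 7.9% |
| 60 | 20.6% | 16.2% |
| 90 | 29.1% | 24.4% |
| 180 | 54.6% | 49.0% |
| 300 | 88.1% | 81.9% |

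**Courses of 14 days or less.** The rule captures none of them, even when they overlap flupirtine completely. This follows from the definition and needs no assumption.

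**Whether other planned outputs fill the gap**

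- The specified co-prescription analysis stops at flupirtine start, so it does not look at the treatment period.
- The concomitant-prescription variable has no window, and its reference for drug classes is Annex 3-ii, which lists pain-related ICD-10 diagnoses and no drugs.
- The concomitant-disease text uses a window of two weeks around flupirtine treatment, while its output line refers to the observation period. Section 8 has co-diagnoses in the analysis period and section 9.3 in the study period. On the two-week reading, a liver diagnosis recorded earlier would be missed.
- NSAID and weak-opioid contraindications, by contrast, have a 12-month look-back, a patient-level percentage and a place in section 9.7.2.4.

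**Comparison list.** Flupirtine contraindications among the six parameters of section 9.7.2.4: 0.

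**The case against.** The strongest reply is that the protocol plans more than the long-term rule. Concomitant prescriptions are a named variable analysed per flupirtine prescription, and section 9.7.1 promises descriptive tables for all variables. Section 9.2 provides for at least 12 months of medical history where available, and the ICD-grouped disease table is not confined to pain diagnoses. Section 9.7.1 also splits every result by period, so the 2012 and 2014 figures will exist side by side in a study without formal tests. Section 9.8 mentions a statistical analysis plan with table shells, where drug lists and windows are often set.

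Much of this stands, and it rules out three stronger readings.

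- A reader might infer that the liver-directed restrictions cannot be assessed at all, or that the pre-treatment co-prescription table is the only other co-medication analysis. The outputs just listed contradict both.
- A reader might take one short course, say 21 days, compute (21 + 14 − 1)/365 = 9.3%, and conclude that about 91% of flagged patients were never exposed concomitantly. That scenario is near the bottom of a category that starts above 14 days. For therapies of 180 to 300 days, 49% to 88% would overlap. Random placement also ignores any link between flupirtine timing and other prescribing.
- A reader might see the Annex 3-ii reference as a decision to analyse co-medication without drugs. A numbering slip is more likely: section 9.3 marks the drug classes with ii and the indication with iii, but the annex has only items i and ii.

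The reply does not rescue the long-term rule. Its duration threshold, missing overlap condition and counted unit are fixed in the protocol, and following them gives the wrong quantity. Tabulating that quantity for both periods shows it twice. A drug code list may properly wait for the analysis plan and is not held against the protocol.

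**Conclusion.** The point holds as a mismatch between a restriction and its measure. As written, section 9.7.2.1 does not estimate how often flupirtine is given together with drugs known to cause liver injury. It misses all overlapping courses of 14 days or less by definition. It includes non-overlapping longer courses to an extent the protocol cannot settle: the overlapping share of flagged therapies runs from about 4% to 88% for lengths of 15 to 300 days. That range assumes random placement, one course of each kind and 14 days of flupirtine. The net direction of the error is unknown.

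Liver disease and alcohol abuse are covered at most inside a general table with inconsistent windows. The omission of all flupirtine contraindications from section 9.7.2.4 is real but less serious, because results by period will still be available.

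**What to change.** 1. In section 9.7.2.1, define contraindicated co-medication as any prescription from a listed set of drugs known to cause liver injury whose supply overlaps the flupirtine prescription length, whatever its duration. Keep more than 14 days as a subgroup.
2. Report it per flupirtine patient, in line with the unit in section 9.7.1 for contraindications, and per flupirtine prescription.
3. Identify pre-existing liver disease and alcohol abuse from ICD-10 codes in the 12 months before exposure start, the same look-back as for NSAID and weak-opioid contraindications. State one window for the general concomitant-disease table.
4. Add both measures, with 95% confidence intervals, to section 9.7.2.4.
5. Give the concomitant-prescription variable a time window, and correct the Annex 3-ii reference so that it leads to a drug-class list.

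Table 1 already holds visit date, product and quantity, ATC code, dosage scheme and ICD-10 code, and section 9.7.2.2 has a method for prescription length that can be extended. The cost is code lists, a few table rows, programming time and assumptions about how long each co-medication supply lasts. Care outside the practice stays invisible (section 9.9), so overlap would still be undercounted to that extent.
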